3.10.2 PK concentrations

Trough PK concentrations of alpelisib and fulvestrant will be summarized by visit and treatment group. Alpelisib sparse PK concentrations will be reported at Cycle 1 Day 15.

Descriptive statistics of concentrations will be provided using steady state concentrations only and include n, number of non-zero concentrations, arithmetic mean, geometric mean, median, SD, coefficient of variation CV (%), geometric CV (%), minimum and maximum. Coefficient of variation CV (%) is calculated as follows from non-zero values: $100 * (\text{SD}/\text{arithmetic mean})$.

Geometric CV (%) is calculated as follows from non-zero values:

[figure not shown]
[figure not shown]
$$\text{CV}(\%) = 100 \cdot \sqrt{\exp(\hat{\sigma}^2) - 1}$$

where $\hat{\sigma}^2$ denotes the variance of the log-transformed values.

Geometric mean and arithmetic mean (SD) plots will also be graphically presented for trough concentration-time data. Individual concentration-time profiles will be displayed graphically for trough concentrations (alpelisib and fulvestrant) and sparse concentrations (alpelisib only) separately. All PK concentration data will be listed as appropriate.

3.10.3 Population PK parameters for alpelisib

The population PK analysis will be conducted in a separate report.

[REDACTED]

[REDACTED]

[REDACTED]

[REDACTED]

[REDACTED]

[REDACTED]

The relationship between alpelisib PK exposure and selected AESI as defined in [Section 3.9.1.5](#)

[REDACTED]

[REDACTED]

3.10.5 Handling missing and invalid values

The lower limits of quantitation (LLOQ) are currently 5.0 ng/mL for alpelisib and 1.0 ng/mL for fulvestrant. Values below the assay LLOQ will be reported as 0 ng/mL. All concentrations below the LLOQ will be displayed in listings as zero with a flag and handled as zero in any calculations of summary statistics, but handled as missing for the calculation of the geometric means and their CV. Any missing PK parameter data will not be imputed.

Invalid concentrations will be flagged in the PK concentration data set by the CP expert after the merge of clinical and bioanalytical data has taken place. Flagged values will not be included in summaries and will be listed only.

[REDACTED]

[REDACTED]

[REDACTED]

[REDACTED]

A 5x5 grid of 25 small images, each showing a different black and white pattern or shape. The patterns include various geometric shapes like squares, rectangles, and L-shapes, some of which are rotated or combined. The images are arranged in a grid with thin black lines separating the cells.

A series of 12 horizontal black bars of varying lengths, decreasing in size from left to right. The bars are evenly spaced and extend across the width of the frame. The first bar is the longest, and the 12th bar is the shortest. The bars are set against a white background.

3.12 Interim analyses

3.12.1 Primary endpoint: Progression-free survival

PIK3CA mutant cohort:

Two interim analyses are planned after approximately 97 and 185 of the 243 targeted PFS events (40% and 76% information fractions respectively) have been documented. These

analyses are expected to take place around 19 and 25 months from the date of first patient randomized in the study. Approximately 243 patients are expected to be randomized when the 97th PFS event occurs at the time of the first interim analysis if H_0 is true (HR.=1). The primary intent of the first interim analysis is to allow the cohort to stop early for lack of efficacy (futility). There is no intent to carry out an analysis to declare superior efficacy at the time of the first interim analysis. The second interim analysis will allow the study to stop early for outstanding efficacy. The second interim analysis will only be carried out after all patients have been randomized in the PIK3CA mutant cohort and approximately 76% of the 243 targeted PFS events have been observed.

The assessment of futility will be guided based on two criteria.

A user-defined gamma spending function ($\gamma=5$) will be used as a beta-spending function to determine the non-binding futility boundary. One important feature of the design is that the efficacy stopping boundaries will not be affected by the presence of non-binding futility stopping boundaries.

Based on the choice of α -spending and β -spending function described above, the futility boundary in terms of p-value scale at the interim is calculated as $p = 0.128$ (or $Z=1.134$; hazard ratio=0.794). The observed (i.e. nominal) p-value has to be greater than 0.128 to conclude futility according to this criterion at the time of the first interim analysis.

In addition to the stopping boundary based on the β -spending function described above, DMC members will be instructed to include in their recommendation whether the conditional probability of observing a clinically relevant PFS treatment effect at the final PFS analysis is less than 0.20, i.e.:

$$\text{Conditional probability } (\text{HR}_{\text{final}} \leq 0.6 | \text{HR}_{\text{interim}}) < 0.20$$

This criterion uses the observed interim data and an assumption regarding the distribution of future unobserved data at the final analysis, conditioned under the alternative hypothesis (HR.=0.6). The futility boundary for this criterion in terms of p-value scale at the interim is calculated as $p=0.068$ (or $|Z|=1.489$; hazard ratio=0.739). Thus the observed (i.e. nominal) p-value has to be greater than the p-value scale futility boundary = 0.068 to conclude futility according to this criterion.

Details of the methodology as well as the operating characteristics for the futility criterion based on conditional probability is described in Section 4.7.

Therefore at the time of the futility analysis, the PIK3CA mutant cohort may be stopped for futility if one or both of the criteria are met.

In addition, the predictive probability of success based on the final planned number of PFS events will be calculated given the interim data, and provided to the DMC at the time of the futility interim analysis as supportive information.

A Haybittle-Peto stopping boundary (as implemented in East 6.3) will be used for interim and final PFS analyses. At the second interim analysis, the observed p-value has to be less than or equal to 0.0001 (or $Z=3.719$) in order to conclude superior efficacy. If the study continues to final analysis, the p-value that will be used to declare statistical significance at the final analysis will be 0.0199 ($Z=2.054$).

Since the observed number of events at the interim analyses may not be exactly equal to the planned number of events, the efficacy and futility boundaries will need to be re-calculated (or updated) based on the actual number of observed events using the pre-specified Haybittle-Peto boundary and β -spending functions. Therefore, the observed p-values at the interim analyses will be compared with the updated boundaries.

If the study continues to final analysis, the p-value that will be used to declare statistical significance at the final analysis will be based on the actual number of PFS events documented at the cut-off date for the final analysis and the alpha already spent at the interim analysis. Therefore, if the interim analyses were carried out after exactly 40% and 76% of the planned number of events, and the cohort continued until the final analysis, the observed p-value will have to be less than 0.0199 to declare statistical significance. If the number of events in the final analysis deviates from the expected number, the final analysis criteria will be determined so that the significance level is maintained at 0.02 in this cohort.

Statistical properties of the group sequential design in this cohort are summarized in [Table 3-10](#).

Table 3-10 Simulated probabilities to stop for futility or efficacy at the interim analysis in the PIK3CA mutant cohort

Scenario	Look	# PFS events	Simulated cumulative probabilities (%)		Simulated incremental probabilities (%)	
			Stop for efficacy	Stop for futility	Stop for efficacy	Stop for futility
Under H_0 (HR=1)	Interim 1	97	0	92.98	0	92.98
	Interim 2	185	0.02	-	0.02	-
	Final	243	0.98	-	0.96	-
Under H_a (HR=0.6)	Interim 1	97	0.34	15.31	0.34	15.31
	Interim 2	185	38.50	-	38.50	-
	Final	243	83.95	-	45.45	-

Note: The study will not stop for outstanding efficacy at the first (futility) interim analysis. Simulation is performed in SAS v9.4 with number of simulations = 10,000 and randomization seed =111064

3.12.2 Key Secondary Endpoint: OS in the PIK3CA mutant cohort

OS will be compared between the two treatment groups, provided the primary endpoint PFS is statistically significant favouring alpelisib. A hierarchical testing procedure will be adopted in this study and OS will be tested only if the primary efficacy endpoint PFS is statistically significant. A maximum of three analyses are planned for OS:

- The first potential time point for OS analysis will be at the time of the PFS efficacy interim analysis after approximately 37% of the expected deaths are observed, at which point approximately 66 deaths are expected. If PFS is not statistically significant at this stage, then OS will not be tested, in which case the next potential time point for OS analysis will be at the time of the final PFS analysis after approximately 57% of the expected deaths are

observed, at which point approximately 101 deaths are expected to have been recorded in the clinical database.

- If OS is not statistically significant at the first interim analysis, the 2nd OS analysis will be planned after approximately 85% of the expected deaths are observed, at which point approximately 151 deaths have been recorded in the clinical database. If OS is not statistically significant at this stage, a final analysis is planned at the time approximately 178 deaths have been recorded.
- If PFS is not statistically significant at the final analysis for PFS, then OS will not be tested.

The type I error probability will be controlled by using a separate Lan-DeMets (O'Brien-Fleming) alpha spending function independent of the Haybittle-Peto boundary used for the primary efficacy analysis of PFS at a 2.0% level of significance for the *PIK3CA* mutant cohort. This guarantees the protection of the overall type I error ($\alpha = 2.5\%$) across all hypotheses and the repeated testing of the OS hypotheses at the interim and the final analyses ([Glimm 2010](#)). This includes hypotheses associated with the secondary endpoints PFS and OS in the *PIK3CA* non-mutant cohort (PFS in the non-mutant cohort will be tested at a 0.5% level of significance if PoC is established). The trial allows for the stopping of a cohort for a superior OS result, provided the primary endpoint PFS has already been shown to be statistically significant favouring the alpelisib arm. Further, the exact nominal p-values that will need to be observed to declare statistical significance at the time of these analyses for OS will depend on the number of OS events that have been observed at the time of these analyses and the α for OS already spent at the time of earlier analyses.

Given the hierarchical testing strategy of PFS and OS, the design concerning OS analyses will have the following characteristics based on simulations in East 6.3. The probabilities shown in [Table 3-11](#) are conditional probabilities (conditional on PFS being statistically significant) not marginal probabilities.

At the final PFS analysis in the *PIK3CA* mutant cohort:

- The cumulative probability to show efficacy on OS (alternative hypothesis H_a is true) by the final analysis is 71.57%; while the cumulative type I error (rejecting the null hypothesis H_0 if H_0 is true) is 1.91%.
- The cumulative probability to detect efficacy on OS if the alternative hypothesis H_a is true is 19.14% at the first interim analysis, 56.60% at the second interim analysis and 71.57% at the final PFS analysis.

Statistical properties the *PIK3CA* mutant cohort are summarized in [Table 3-11](#).

Table 3-11 Simulated probabilities to stop for efficacy at 1st interim, 2nd interim, or final OS analysis in the *PIK3CA* mutant cohort

Scenario	Look	# deaths	Simulated cumulative probabilities (%) [*]	Simulated incremental probabilities (%) [*]
			Stop for efficacy	Stop for efficacy
Scenario 1: The first IA for OS is performed at the time of the PFS IA for efficacy				
Under H_0 (HR.=1)	1st Interim	66	0.01	0.01

Scenario	Look	# deaths	Simulated cumulative probabilities (%) [*]	Simulated incremental probabilities (%) [*]
			Stop for efficacy	Stop for efficacy
	2nd Interim	151	1.11	1.09
	Final OS	178	1.89	0.79
Under H_0 (HR.=0.67)	1st Interim	66	1.94	1.94
	2nd Interim	151	57.01	55.07
	Final OS	178	71.62	14.61
Scenario 2: The first IA for OS is performed at the time of the final PFS analysis				
Under H_0 (HR.=1)	1st Interim	101	0.17	0.17
	2nd Interim	151	1.12	0.95
	Final OS	178	1.91	0.79
Under H_a (HR.=0.67)	1st Interim	101	19.14	19.14
	2nd Interim	151	56.60	37.46
	Final OS	178	71.57	14.97

Note: Simulations are performed in East 6.3 with number of simulations = 10,000 and randomization seed =37059.

* Probabilities are reported as if OS was tested alone, regardless the testing strategy with PFS. The true probabilities should take into account the probability of PFS at each look. Simulated probabilities shown based on the alpha allocated for testing (p=0.02).

At the time of final PFS analysis in this cohort, both PFS and interim OS analysis will be performed by the Sponsor's clinical team. Investigators and patients will remain blinded to study treatment and all patients will continue to be followed for OS until the final OS analysis (or earlier if OS reaches statistical significance at any of the interim analyses).

3.12.3 OS in the PIK3CA non-mutant cohort:

OS will be compared between the two treatment groups, provided the PFS is statistically significant favouring alpelisib, in the *PIK3CA* non-mutant cohort. A hierarchical testing procedure will be adopted in this study and the OS analyses will be tested only if PFS is statistically significant. A maximum of three analyses are planned for OS:

- at the time of the final analysis for PFS (provided PFS is statistically significant) when approximately 29% of the expected deaths are observed, at which point approximately 36 deaths in the *PIK3CA* non-mutant cohort have been recorded (after approximately 18 months from the first patient to be randomized in this cohort);
- at the time when approximately 87% of the expected deaths are observed, at which point approximately 109 deaths in the *PIK3CA* non-mutant cohort have been recorded (after approximately 45 months from the first patient to be randomized in this cohort);
- a final analysis for OS when approximately 125 deaths in the *PIK3CA* non-mutant cohort have been recorded (approximately 54 months from date of first patient to be randomized in this cohort).

An α -spending function according to Lan-DeMets (O'Brien-Fleming will be used to maintain the overall type I error probability ([Lan and DeMets 1983](#)). The exact nominal p-values that will need to be observed to declare statistical significance at the time of these analyses for OS

will depend on the number of OS events that have been observed at the time of these analyses and the α for OS already spent at the time of earlier analyses.

Given the hierarchical testing strategy of PFS and OS, the design concerning OS analyses will have the following characteristics based on simulations in East 6.3. The probabilities shown in [Table 3-12](#) are conditional probabilities (conditional on PFS being statistically significant) not marginal probabilities.

Table 3-12 Simulated probabilities to stop for efficacy at 1st interim, 2nd interim, or final OS analysis in the PIK3CA non-mutant cohort

Scenario	Look	# deaths	Simulated cumulative probabilities (%) [*]	Simulated incremental probabilities (%) [*]
			Stop for efficacy	Stop for efficacy
Under H_0 (HR.=1)	1st Interim	36	<0.001	<0.001
	2nd Interim	109	0.31	0.31
	Final OS	125	0.59	0.28
Under H_a (HR.=0.67)	1st Interim	36	0.001	0.001
	2nd Interim	109	24.59	24.58
	Final OS	125	36.74	12.15

Note: Simulations are performed in East 6.3 with number of simulations = 10,000 and randomization seed =60030. 1st Interim analysis will be conducted at the time of final analysis for PFS

* Probabilities are reported as if OS was tested alone, regardless the testing strategy with PFS. The true probabilities should take into account the probability of PFS at each look. Simulated probabilities shown based on the alpha allocated for testing (p=0.005).

At the time of final PFS analysis in this cohort, both PFS and interim OS analysis will be performed by the independent statistical group for the DMC. The Novartis Clinical team will remain blinded to study treatment allocations up until such point the PIK3CA mutant cohort can be unblinded. Investigators and patients will remain blinded to study treatment and all patients will continue to be followed for OS until the final OS analysis (or earlier if OS reaches statistical significance at any of the interim analyses).

3.12.4 Confidentiality of Interim OS results

At the time of final PFS analysis in the PIK3CA mutant cohort, both PFS and interim OS analysis will be performed by the Sponsor's clinical team. Investigators and patients will remain blinded to study treatment and all patients will continue to be followed for OS until the final OS analysis (or earlier if OS reaches statistical significance at any of the interim analyses).

3.13 Subgroup analysis

3.13.1 Safety

The objective for carrying out these subgroup analyses is to identify potential safety issues that may be limited to a subgroup of patients, or safety issues that are more commonly observed in a subgroup of patients

The main safety analyses will be repeated in the following subgroups of patients:

- Age ≥ 65 vs age < 65 years
- Age ≥ 75 vs age < 75 years
- Race (white vs Asian vs black or African American vs other)

[figure not shown]
These main safety analyses include:

- AEs, by SOC, PT, maximum CTCAE grade
- Treatment-related AEs by SOC, PT, maximum CTCAE grade
- Serious adverse events (SAE) by SOC, PT, maximum CTCAE grade
- •
- For the AESI of Hyperglycemia only, a subgroup analysis by hyperglycemia diagnosis status at baseline per American Diabetes Association (ADA) 2017 will be presented:
 - Diabetic: FPG ≥ 7.0 mmol/l or 126 mg/dl or HbA1c ≥ 6.5 % vs.
 - Pre-diabetic: FPG 5.6- < 7.0 mmol/l or 100-125 mg/dl or HbA1c 5.7- < 6.5 % vs.
 - Normal: [FPG < 5.6 mmol/l or < 100 mg/dl] and HbA1c < 5.7 %

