- In absence of liver metastases, ALT and AST $\leq 2.5 \times \text{ULN}$. If the patient has liver metastases, ALT and AST $\leq 5 \times \text{ULN}$
- Total bilirubin $< \text{ULN}$ except for patients with Gilbert's syndrome who may only be included if the total bilirubin is $\leq 3.0 \times \text{ULN}$ or direct bilirubin $\leq 1.5 \times \text{ULN}$
- Fasting plasma glucose (FPG) $\leq 140 \text{ mg/dL}$ (7.7 mmol/L)* and Glycosylated Hemoglobin (HbA1c) $\leq 6.4\%$ (both criteria have to be met)
- Fasting Serum amylase $\leq 2 \times \text{ULN}$
- Fasting Serum lipase $\leq \text{ULN}$

*For patients with FPG $\geq 100 \text{ mg/dL}$ and/or HbA1c $\geq 5.7\%$ (i.e. threshold for pre-diabetes) at screening, -recommend lifestyle changes according to ADA guidelines, i.e. dietary advice (e.g. small frequent meals, low carbohydrate content, high fiber, balancing carbohydrate intake over the course of the day, three small meals and 2 small snacks rather than one large meal) and exercise. A consultation with a diabetologist is highly recommended.

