5.3 Exclusion criteria

Patients eligible for this study must not meet **any** of the following criteria:

1. Patient with symptomatic visceral disease or any disease burden that makes the patient ineligible for endocrine therapy per the investigator's best judgment.
2. Patient has received prior treatment with chemotherapy (except for neoadjuvant/ adjuvant chemotherapy), fulvestrant, any PI3K, mTOR or AKT inhibitor
3. Patient has a known hypersensitivity to alpelisib or fulvestrant, or to any of the excipients of alpelisib or fulvestrant.
4. Patient with inflammatory breast cancer at screening.
5. Patient is concurrently using other anti-cancer therapy.
6. Patient has had surgery within 14 days prior to starting study drug or has not recovered from major side effects.
7. Patient has not recovered from all toxicities related to prior anticancer therapies to NCI CTCAE version 4.03 Grade ≤ 1 . Exception to this criterion: patients with any grade of alopecia are allowed to enter the study.
8. Patients with Child pugh score B or C.

9. Patient has received radiotherapy \leq 4 weeks or limited field radiation for palliation \leq 2 weeks prior to randomization, and who has not recovered to grade 1 or better from related side effects of such therapy (with the exception of alopecia) and/or from whom \geq 25% of the bone marrow was irradiated.
10. Patient has a concurrent malignancy or malignancy within 3 years of randomization, with the exception of adequately treated, basal or squamous cell carcinoma, non-melanomatous skin cancer or curatively resected cervical cancer.
11. Patient has central nervous system (CNS) involvement
If patient is fulfilling the following 3 criteria she/he is eligible for the trial.
 - completed prior therapy (including radiation and/or surgery) for CNS metastases \geq 28 days prior to the start of study and
 - Central Nervous System (CNS) tumor is clinically stable at the time of screening and
 - patient is not receiving steroids and/or enzyme inducing anti-epileptic medications for brain metastases
12. Patients with an established diagnosis of diabetes mellitus type I or not controlled type II (based on FPG and HbA1c, see inclusion criterion 12)
13. Patient has impairment of gastrointestinal (GI) function or GI disease that may significantly alter the absorption of the study drugs (e.g., ulcerative diseases, uncontrolled nausea, vomiting, diarrhea, malabsorption syndrome, or small bowel resection)

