6.3.2.1.3 Guidelines for the treatment of alpelisib induced hyperglycemia

Alpelisib, like other PI3K inhibitors, may affect glucose homeostasis which could result in increases of plasma glucose and insulin resistance (Busaidy 2012). Alpelisib induced hyperglycemia is generally manageable with adequate antidiabetic treatment. Alpelisib induced hyperglycemia typically occurs within the first month of treatment. Patients with pre-diabetes (i.e. FPG 100 – 125 mg/dl; 5.6 - 6.9 mmol/L) and those with an established diagnosis of type 2 diabetes mellitus should be monitored carefully, thus allowing an early detection and prompt management of increases in FPG while on alpelisib/placebo treatment. However all patients, even those with FPG within normal limits at screening, may develop alpelisib induced hyperglycemia. Patients should always be instructed to follow dietary guidelines provided by the American Diabetes Association, e.g. small frequent meals, low carbohydrate content, high fiber, balancing carbohydrates over the course of the day; three small meals and 2 small snacks rather than one large meal and exercise, as appropriate.

Detailed guidelines for management of alpelisib induced hyperglycemia is provided in [Table 6-3](#) following discussion with an advisory board. This includes early administration of metformin. Metformin may be titrated to a daily dose of 1000 mg BID. Local protocols per standard clinical practice may be followed for monitoring and managing hyperglycemia. Fasting plasma glucose may be performed both locally and/or centrally for rapid availability for safety evaluation and management guidance. Special attention should be paid to the risk of hypoglycemia in patients interrupting alpelisib treatment and concomitantly receiving insulin and/or sulfonylureas. Due to the short half-life of alpelisib, all glucose lowering medications should be discontinued when alpelisib is stopped.

Consultation with a diabetologist is highly recommended for better assessment and management of alpelisib-induced hyperglycemia.

6.3.2.1.4 .Follow-up on amylase or lipase elevation (\geq CTCAE Grade 3)

Patient with amylase or lipase elevation \geq CTCAE Grade 3 must be tested weekly (or more frequently if clinically indicated) until \leq Grade 1 (or baseline). After resumption of dosing, continue to test weekly for one additional cycle. If no reoccurrence of \geq Grade 2 event, continue monitoring every cycle.

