3.6.1 Duration of study treatment exposure

Duration of exposure to study drug (for alpelisib/placebo and fulvestrant) is defined according to dosing regimen for each study drug as outlined in [Section 2.1.6](#).

Duration of exposure (days) = (last date of exposure to study drug) – (date of first administration of study drug) + 1

Duration of exposure to study treatment is considered by taking into account the duration of exposure to each study drug:

Duration of exposure (days) = (last date of exposure to study treatment) – (date of first administration of study treatment) + 1,

The duration includes the periods of temporary interruption. ‘Date of first administration of study drug/treatment’ and ‘last date of exposure to study drug/treatment’ are defined in Sections [2.1.2/2.1.4](#) and [2.1.6 respectively](#).

Duration of exposure to study drug/treatment will be categorized into time intervals (<1 month, at least 1 month, at least 2 months etc.). In addition, summary statistics will be displayed.

Note: If the last record in DAR CRF is a zero dose, this record will not be used in the analyses.

To assess the impact of specific adverse events of special interest on exposure to study treatment the following summaries are added:

- Duration of exposure to study drug for patients who developed hyperglycemia during the study

- Duration of exposure to study drug for patients who developed hyperglycemia during the study and started anti-diabetic medication
- Duration of exposure to study drug for patients who developed hyperglycemia during the study and started anti-diabetic medication by hyperglycemia diagnosis status
- Duration of exposure to study drug for patients who developed rash during the study
- Duration of exposure to study drug for patients who developed rash during the study and started anti-rash medication

Patients who developed hyperglycemia [rash] during the study are defined as those patients with any on-treatment CTC Grade 1 or higher AESI. Hyperglycemia diagnosis status is defined in Section [3.13.1](#). Anti-diabetic medications are defined by medications where ATC code=A10 [Drugs used in diabetes]. Anti-rash medications are defined by medications where ATC codes in the following categories:

- R06A [Antihistamines for systemic use]
- D07 [Topical dermatological corticosteroids]
- H02 [Corticosteroids systemic]

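### The SAP's baseline 'hyperglycemia diagnosis status' uses laboratory values only, so known type 2 diabetics with FPG below 126 mg/dL and HbA1c below 6.5% are analysed as pre-diabetic or normal

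*SAP*

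**What the plan says.** SAP 3.13.1 explains that its safety subgroups are there to find problems confined to, or more frequent in, some patients. For the hyperglycemia AESI it adds that "a subgroup analysis by hyperglycemia diagnosis status at baseline per American Diabetes Association (ADA) 2017 will be presented". The classes are:

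- Diabetic: FPG at or above "7.0 mmol/l or 126 mg/dl or HbA1c" at or above 6.5%.
- Pre-diabetic: FPG from 5.6 to below "7.0 mmol/l or 100-125 mg/dl or HbA1c 5.7" to below 6.5%.
- Normal: FPG below 5.6 mmol/l or below "100 mg/dl] and HbA1c" below 5.7%.

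No class refers to a recorded diagnosis or to treatment. SAP 3.6.1 reuses the variable ("Hyperglycemia diagnosis status is defined in Section" 3.13.1) to split duration of exposure among patients who developed hyperglycemia and started anti-diabetic medication.

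Protocol 5.3, criterion 12, excludes "Patients with an established diagnosis of diabetes mellitus type I or not controlled type II", with control judged on FPG and HbA1c. Protocol 5.2, criterion 12, sets the limits at FPG 140 mg/dL and HbA1c 6.4%, and "both criteria have to be met". Controlled type 2 diabetes is therefore eligible. Protocol 6.3.2.1.3 expects such patients: besides those with pre-diabetes, it says that "those with an established diagnosis of type 2 diabetes mellitus should be monitored carefully".

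**The concern.** The variable is named for a diagnosis but does not use one. The protocol treats pre-diabetes and established type 2 diabetes as two separate groups. The SAP separates them only by the laboratory values at entry, and eligibility selects known diabetics for low values. A patient whose diabetes is well controlled is thus counted among patients who never had the disease.

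Hyperglycemia is a designated AESI and was the most common drug-related grade 3 or 4 event with single-agent alpelisib (24%, Protocol 1.2.2.2). A reader will use this table to see how patients with diabetes fared against those without. If known diabetics sit in all three classes, the table cannot answer that question and the contrast between classes may be blurred. The same applies to the exposure summary in SAP 3.6.1, where pre-existing diabetes bears directly on what is being described.

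**Working it through.** The plan gives no figure to reproduce. The check is to overlay the SAP classes on the entry limits.

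**Inputs.** Entry limits: FPG ≤140 mg/dL and HbA1c ≤6.4% (Protocol 5.2, criterion 12). Class limits: 126 and 100 mg/dL for FPG, 6.5% and 5.7% for HbA1c (SAP 3.13.1). Baseline is taken to lie within the entry limits. SAP 2.1.8 uses the last value on or before the start of treatment, so an unscheduled repeat could in principle fall outside them.

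**Rules as written.**
- Diabetic: FPG ≥126 or HbA1c ≥6.5.
- Pre-diabetic: 100 ≤ FPG < 126 or 5.7 ≤ HbA1c < 6.5.
- Normal: FPG < 100 and HbA1c < 5.7.

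**Step 1: which routes to Diabetic remain open?** With HbA1c ≤6.4%, the HbA1c route is closed. Only FPG 126-140 mg/dL is left.

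**Step 2: where does a known, eligible type 2 diabetic land?**

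| FPG (mg/dL) | HbA1c (%) | Class or classes met |
|---|---|---|
| 95 | 5.5 | Normal |
| 95 | 6.2 | Pre-diabetic |
| 125 | 6.4 | Pre-diabetic |
| 126 | 5.5 | Diabetic |
| 130 | 6.2 | Diabetic and Pre-diabetic |

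**Step 3: check over the whole eligible region.** I took FPG 70-140 in steps of 1 (71 values) and HbA1c 4.5-6.4 in steps of 0.1 (20 values), giving 71 × 20 = 1,420 combinations. The lower ends, 70 and 4.5, are assumptions that do not affect the conclusion.
- FPG 126-140: 15 × 20 = 300 combinations meet Diabetic, none of them through HbA1c.
- FPG below 100 with HbA1c below 5.7: 30 × 12 = 360 are Normal.
- The other 1,420 − 300 − 360 = 760 are Pre-diabetic.
- FPG 126-140 with HbA1c 5.7-6.4: 15 × 8 = 120 of the 300 meet Diabetic and Pre-diabetic together. SAP 3.13.1 states no order of precedence.

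These are counts of value combinations, not proportions of patients.

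**Step 4: who was actually enrolled?** The 6.4% limit came with Protocol Amendment 2, dated 30 August 2016. By 19 August 2016, 317 patients had been randomised, and 317/572 = 55% of the final total. Amendment 1 had set the limit at 6.5%; the limit before that is not stated in the text. Some analysed patients may therefore reach Diabetic through HbA1c. How many is not given.

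**Step 5: are the missing data available?** Yes. Current medical conditions and medications taken within 30 days before the first dose are collected (Protocol 7.1.1.3). Medical history is coded in MedDRA (SAP 3.2.3), concomitant medication in ATC (SAP 3.7), and anti-diabetic medication is already defined as ATC A10 (SAP 3.6.1).

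**The case against.** The best defence is that a class based on baseline glycemia is explicit and reasonable. The cut-offs are printed beside the label. The protocol itself tends to express risk in laboratory terms: the rationale for Amendment 1 links excess grade 3/4 hyperglycemia to HbA1c between 6.5 and 8.0%, and control of type 2 diabetes is judged on FPG and HbA1c. Whether the cited ADA classification also counts prior diagnosis cannot be settled from these documents. The tables are descriptive, and medical history and concomitant medication are reported elsewhere. Also, use of an A10 drug at baseline is not a diagnosis: Protocol 5.2 recommends a diabetologist consultation at screening for patients in the pre-diabetic range, and some of them could start such a drug before dosing.

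Much of this stands. The laboratory grouping is worth keeping, the effect is small in scope, and A10 use should not define the class by itself. What does not stand is the label. A reader of a table by diagnosis status will take Normal to mean no known diabetes, and the separate listings do not cross known diabetes with the AESI.

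A reader might also infer more than the documents support:
- *That all controlled type 2 diabetics are misclassified.* They are not. Those with FPG 126-140 mg/dL meet the Diabetic definition.
- *That the HbA1c route is closed for the whole analysed population.* It is closed under the current criteria, but at least 317 patients entered before that limit applied.
- *That the Diabetic class lacks most diabetics, or that the number misplaced can be estimated.* The documents give neither the number of patients with known type 2 diabetes nor their FPG values.
- *That risk in the lower classes is inflated.* It may be, but no event rate for controlled diabetics is given.

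**Conclusion.** The concern holds in a limited form. Eligible patients with established type 2 diabetes, baseline FPG below 126 mg/dL and HbA1c below 6.5% are analysed as pre-diabetic or normal in the hyperglycemia AESI subgroup (SAP 3.13.1) and in the related exposure summary (SAP 3.6.1). This follows from the definitions and the eligibility criteria and needs no assumption about prevalence. The number affected cannot be derived from the documents.

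The consequence is confined to descriptive safety tables, where the contrast between classes may be blurred. No test, significance level, power figure or efficacy result is touched. The overlap between Diabetic and Pre-diabetic is a second, smaller defect in the same definition. The change should be made because the table concerns a main toxicity and the remedy is cheap, but nothing else in the plan depends on it.

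**What to change.** In SAP 3.13.1, and through it in SAP 3.6.1:

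1. Define Diabetic as a recorded medical history of diabetes mellitus, or FPG ≥126 mg/dL, or HbA1c ≥6.5%. Alternatively, keep the three laboratory classes and show known diabetes as a row of its own.
2. Assign each patient to the highest class met, so that FPG 130 mg/dL with HbA1c 6.2% has one answer.
3. Use A10 medication ongoing at baseline only as supporting evidence for a history of diabetes, or in a sensitivity version of the table.
4. Keep the laboratory-only grouping as a supplementary table, renamed 'baseline glycemic category'.

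The cost is one extra derivation and one extra table, from data already collected and coded. Eligibility, treatment and patient management do not change.
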